9.2.2 Reporting Procedures for Serious Adverse Events

The investigator is responsible for ensuring that all serious adverse events observed by the investigator or reported by the subject that occur after signing of the informed consent through 30 days after the last dose of IP or EOS, whichever is later, are recorded in the subject's medical record and are submitted to Amgen. All serious adverse events must be submitted to Amgen within 24 hours following the investigator's knowledge of the event via the applicable eCRF.

After the protocol-required reporting period defined above, the investigator does not need to actively monitor subjects for serious adverse events. However, if the investigator becomes aware of a serious adverse event after this protocol-required reporting period, the investigator will report the event to Amgen within 24 hours following the investigator's knowledge of the event. Serious adverse events reported outside of the protocol-required reporting period will be captured within the safety database as clinical trial cases for the purposes of expedited reporting.

If the electronic data capture (EDC) system is unavailable to the site staff to report the Serious Adverse Event, the information is to be reported to Amgen via an electronic Serious Adverse Event (eSAE) Contingency Report Form within 24 hours of the investigator's knowledge of the event. See Appendix B for a sample of the Serious Adverse Event Worksheet/electronic Serious Adverse Event Contingency Report Form. If the first notification of a Serious Adverse Event is reported to Amgen via the eSerious Adverse Event (eSAE) Contingency Report Form, the data must be entered into the EDC system when the system is again available.

The investigator must assess whether the serious adverse event is possibly related to IP (evolocumab or placebo). This relationship is indicated by a "yes" or "no" response to

the question: Is there a reasonable possibility that the event may have been caused by IP?

The investigator must assess whether the serious adverse event is possibly related to the prefilled AI/Pen or 3.5 mL Personal Injector **device** used to administer IP. The relationship is indicated by a "yes" or "no" response to the question: Is there a reasonable possibility that the event may have been caused by the device?

The investigator must assess whether the serious adverse event is possibly related to any other study-mandated activity (eg, screening / lipid stabilization procedure or background therapy). This relationship is indicated by a "yes" or "no" response to the question: "Is there a reasonable possibility that the event may have been caused by another study activity (eg, screening / lipid stabilization procedure or background therapy)?"

The investigator is expected to follow reported serious adverse events until stabilization or reversibility. If the severity of a serious adverse event worsens from the date of onset to the date of resolution, record a single event for each increased level of severity on the Adverse Event eCRF.

New information relating to a previously reported serious adverse event must be submitted to Amgen. All new information for serious adverse events must be sent to Amgen within 24 hours following knowledge of the new information. The investigator may be asked to provide additional follow-up information, which may include a discharge summary or extracts from the medical record. Information provided about the serious adverse event must be consistent with that recorded on the applicable CRF (eg, Adverse Event Summary CRF).

If a subject is permanently withdrawn from protocol-required therapies because of a serious adverse event, this information must be submitted to Amgen.

To comply with worldwide reporting regulations for serious adverse events, the treatment assignment of subjects who develop serious, unexpected, and related adverse events may be unblinded by Amgen before submission to regulatory authorities. Investigators will receive notification of related serious adverse events reports sent to regulatory authorities in accordance with local requirements.

Amgen will report serious adverse events and/or suspected unexpected serious adverse reactions as required to regulatory authorities, investigators/institutions, and IRBs/IECs

in compliance with all reporting requirements according to local regulations and good clinical practice.

The investigator is to notify the appropriate IRB/IEC of serious adverse events occurring at the site and other adverse event reports received from Amgen, in accordance with local procedures and statutes.

9.3 Pregnancy and Lactation Reporting

If a pregnancy occurs in a female subject, or female partner of a male subject, while the subject is taking protocol-required therapies report the pregnancy to Amgen as specified below.

In addition to reporting any pregnancies occurring during the study, investigators should monitor for pregnancies that occur after the last dose of protocol-required therapies through 15 weeks after the end of treatment with IP.

The pregnancy should be reported to Amgen **Global Patient Safety** within 24 hours of the investigator's knowledge of the event of a pregnancy. Report a pregnancy on the Pregnancy Notification Worksheet (Appendix C).

If a lactation case occurs while the female subject is taking protocol-required therapies report the lactation case to Amgen as specified below.

In addition to reporting a lactation case during the study, investigators should monitor for lactation cases that occur after the last dose of protocol-required therapies through 15 weeks after the end of treatment with IP.

Any lactation case should be reported to Amgen **Global Patient Safety** within 24 hours of the investigator's knowledge of event. Report a lactation case on the Lactation Notification Worksheet (Appendix C).

10. STATISTICAL CONSIDERATIONS

- 10.1 Study Endpoints, Analysis Sets, and Covariates
- 10.1.1 Study Endpoints
- 10.1.1.1 Co-primary Efficacy Endpoints
- mean percent change from baseline in LDL-C at weeks 10 and 12
- percent change from baseline in LDL-C at week 12

10.1.1.2 Co-secondary Efficacy Endpoints

Co-secondary efficacy endpoints are (1) the mean of weeks 10 and 12 and (2) week 12 for:

Tier 1 endpoints

- change from baseline in LDL-C
- percent change from baseline in non-HDL-C
- percent change from baseline in ApoB100
- percent change from baseline in the total cholesterol
- percent change from baseline in the total cholesterol/HDL-C ratio
- percent change from baseline in ApoB100/ApoA1 ratio
- achievement of target LDL-C < 70 mg/dL (1.8 mmol/L)

Tier 2 endpoints

- percent change from baseline in Lp(a)
- percent change from baseline in triglycerides
- percent change from baseline in HDL-C
- percent change from baseline in VLDL-C

10.1.1.3 Co-tertiary Efficacy Endpoints

 mean percent change from baseline at weeks 10 and 12 and percent change from baseline at week 12 in ApoA1

10.1.1.4 Exploratory Endpoints

- subject incidence of non-coronary revascularization
- change and percent change from baseline at each scheduled assessment in each of the following parameters:
 - LDL-C
 - total cholesterol
 - non-HDL-C
 - ApoB100
 - total cholesterol/HDL-C ratio
 - ApoB100/ApoA1 ratio
 - VLDL-C
 - HDL-C
 - ApoA1

- triglycerides
- Lp(a)
- hsCRP at each scheduled assessment
- HbA1c at each scheduled assessment
- PCSK9 change from baseline at each scheduled assessment
- fasting and post-prandial laboratory parameters of interest (including MMTT Extended Timepoints Substudy assessments)

10.1.1.5 Safety Endpoints

- subject incidence of treatment emergent adverse events
- safety laboratory values and vital signs at each scheduled assessment
- ECG parameters (such as RR, PR, QRS, QT and QTc intervals) at each scheduled assessment
- incidence of anti-evolocumab antibody (binding and neutralizing) formation

10.1.1.6 Pharmacokinetics Endpoints

• serum concentration of evolocumab at selected time points

10.1.2 Analysis Sets

The full analysis set (FAS) includes all randomized subjects who received at least 1 dose of IP. This analysis set will be used in both efficacy and safety analyses. In efficacy analyses, subjects will be grouped according to their randomized treatment group assignment. For safety analyses, subjects will be grouped according to their randomized treatment group assignment with the following exception: if a subject receives treatment throughout the study that is different than the randomized treatment group assignment, then the subject will be grouped by the actual treatment group.

The completer analysis set (CAS) includes subjects in the FAS who adhered to the scheduled IP regimen and have observed value for the co-primary endpoints.

10.1.3 Covariates and Subgroups

Baseline covariates include, but are not limited to:

- stratification factors:
 - statin therapy at study entry (no statin use vs non-intensive statin use vs intensive statin use [see Appendix D]
 - site's geographic region
- age: < 65 years, ≥ 65 years
- sex
- race

- baseline LDL-C: < median, ≥ median
- family history of premature coronary heart disease: yes, no
- baseline PCSK9 level: < median, ≥ median

10.2 Sample Size Considerations

The sample size is 300 subjects for each of the evolocumab SC in combination with atorvastatin arms, and 150 subjects for each of the placebo in combination with atorvastatin arms. The sample size should provide adequate power to determine the superiority of evolocumab in combination with atorvastatin to placebo in combination with atorvastatin as measured by the co-primary endpoints in both dose frequencies using the FAS. The primary analysis will require the tests of each co-primary endpoint to be significant at a level of 0.05 (Section 10.5). From the global phase 2 studies in the evolocumab program, the treatment effect measured as the mean of week 10 and week 12 were as large or larger than week 12 and highly correlated (> 85%) with ones at week 12. From the global phase 2 study 20110155, the treatment effects (on top of stable background statin therapy) of evolocumab compared to placebo for 140 mg Q2W and 420 mg QM in the mean percent change from baseline in LDL-C are -66.10 (95% CI [-71.48,-60.72]) and -50.33 (95% CI [-56.04,-44.62]) at week 12, respectively and the observed evolocumab dose group means in the type 2 diabetes mellitus cohort were comparable to the overall population. The power calculation is derived assuming a treatment effect in the percent reduction of LDL-C of at least 35% at week 12 in each dose frequency, with a common standard deviation (SD) of 20%. It is assumed that approximately 15% of subjects randomized into IP will end IP early, thus attenuating the treatment effects. It is assumed there will be no treatment effect differences among treatment groups after these subjects end IP early. After accounting for treatment attenuation due to early IP termination, the assumed treatment effect is a 30% reduction in LDL-C with a common SD of 30%. Assuming 2% of randomized subjects do not receive any IP, the planned sample size will provide at least 99% power in testing the superiority of evolocumab in combination with atorvastatin to placebo in combination with atorvastatin at week 12 in each dose frequency. Therefore, the sample size as planned will provide at least 98% (99% x 99%) power for the co-primary endpoints in each of the dose frequencies.

Since the testing statistics from the Q2W and QM groups are independent, there is approximately a 96% (98% x 98%) chance to show the superiority of both dose frequencies for the co-primary endpoints.

Sample size assumptions, such as the missing value rate, will be monitored by the study team while maintaining study blind.

The power calculation is derived using nQuery version 7.01.

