10.1 General Principles

The final analysis will be conducted when all subjects have either completed all the scheduled study visits or have early terminated from the study. At that time, the database will be cleaned, processed and a snapshot will be taken; the study will also be unblinded. Based on the snapshot, efficacy and safety analyses will be performed on the FAS. Unless specified otherwise, the FAS will be the default analysis set in this study and data will be summarized by randomized treatment group.

Analyses will be performed separately by each dose frequency (Q2W and QM) as two separate trials unless specified otherwise. Differences in model estimates between evolocumab QM and evolocumab Q2W and associated confidence intervals for the differences will be calculated for each lipid parameter. The superiority of evolocumab to placebo will be assessed for all efficacy endpoints. Unless specified otherwise, all other hypothesis testing will be 2-sided with a significance level of 0.05.

Subject disposition, demographics, baseline characteristics, and exposure to IP will be summarized.

Summary statistics for continuous variables will include the number of subjects, mean, median, standard deviation or standard error, minimum, and maximum. For categorical variables, the frequency and percentage will be summarized.

Multiplicity Adjustment Method

In order to preserve the familywise error rate at 0.05, each independent dose frequency (Q2W and QM) will be allocated a significance level of 0.05 for the co-primary endpoints. For FAS, methods of adjusting for multiplicity due to testing the superiority of evolocumab in combination with atorvastatin to placebo in combination with atorvastatin for both the co-primary and co-secondary efficacy endpoints within each dose frequency are described in the diagram below.

The testing strategy outlined in the diagram will be executed two times: once for each IP dose frequency for testing versus placebo. Within each IP dose frequency, testing of each co-endpoint pair will result in a single p-value (see Table 2 for more details), and for co-secondary endpoints these p-values will then be used in the Hochberg procedure. The following method will be used to preserve the family wise error rate for co-primary and co-secondary efficacy endpoints for testing within each IP dose frequency:

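### The overall success probability of about 96% in Protocol 10.2 and SAP 3.2 is a lower bound worded as an estimate; the plan's own inputs give above 99.99%

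*Protocol*

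**What the plan says.** Protocol 10.2 and SAP 3.2 carry the same sample size text. Its inputs are:

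- **Allocation:** "The sample size is 300 subjects for each of the evolocumab SC in combination with atorvastatin arms, and 150 subjects for each of the placebo" arms.
- **Effect before attenuation:** "at least 35% at week 12 in each dose frequency, with a common standard deviation (SD) of 20" percent.
- **Early stopping of IP:** "approximately 15% of subjects randomized into IP will end IP early", with no treatment difference assumed afterwards.
- **Effect used for power:** "the assumed treatment effect is a 30% reduction in LDL-C with a common SD of 30" percent.
- **Never dosed:** 2% of randomized subjects.
- **Success criterion:** "The primary analysis will require the tests of each co-primary endpoint to be significant at a level of 0.05".

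From these the text moves in three steps. It gives power of at least 99% for the week 12 test in each dose frequency. It multiplies 99% by 99% to reach at least 98% for the co-primary pair in each frequency. It then says the Q2W and QM statistics are independent and concludes that "there is approximately a 96% (98% x 98%) chance to show the superiority of both dose frequencies".

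The same paragraph reports that in phase 2 the effects on the mean of weeks 10 and 12 were no smaller than those at week 12 and "highly correlated (> 85%) with ones at week 12".

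**The concern.** The first two steps are worded as minimum values. The third multiplies those minimum values but presents the result as an approximation. Multiplying lower bounds can only give another lower bound. It cannot say roughly how large the probability is.

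This is where the two documents state the chance of success in both frequencies. Taken at face value it is an estimate, and it should then follow from the effect, SD, sample size and alpha printed a few lines above. It does not. What is at stake is the accuracy of a stated design figure; no analysis uses it.

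**Working it through.** **1. Reproduce the plan's figure.** 0.99 × 0.99 = 0.9801, given as 98%. 0.98 × 0.98 = 0.9604, given as 96%. The figure reproduces, but only as a product of floors.

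**2. Inputs for a direct calculation.**
- Analysed subjects per frequency: 300 × 0.98 = 294 evolocumab and 150 × 0.98 = 147 placebo.
- Effect 30 points, SD 30 (Protocol 10.2). The 30 is 35 × 0.85 = 29.75, rounded.
- Two-sided alpha of 0.05 per test. SAP 10.1 says "all other hypothesis testing will be 2-sided with a significance level of 0.05", and the alternative hypothesis in SAP section 5 has no direction.
- Mean of weeks 10 and 12: effect at least 30, since phase 2 showed effects no smaller than at week 12. The documents give no SD for this endpoint. **Assumption:** 30, as at week 12.

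**3. Power per test (two-sample comparison).**
- SE = 30 × √(1/294 + 1/147) = 3.03
- Noncentrality = 30 / 3.03 = 9.90
- Chance of missing = Φ(1.96 − 9.90) = Φ(−7.94) ≈ 1.0 × 10⁻¹⁵ (noncentral t with 439 df: 1.2 × 10⁻¹⁵)

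**4. Joint success on all four tests.** By the Bonferroni inequality, P(all four succeed) ≥ 1 − 4 × 1.0 × 10⁻¹⁵, or about 1 − 4 × 10⁻¹⁵. This holds under any correlation. Tails this small should not be read literally for planning values; the usable statement is *above 99.99%*.

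**5. Sensitivity: chance of missing one test when one input is changed.**

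| Change | Miss probability per test |
|---|---|
| 300 vs 150, no loss | 4.5 × 10⁻¹⁶ |
| Effect 29.75 | 2.0 × 10⁻¹⁵ |
| Two-sided alpha 0.01 | 1.2 × 10⁻¹³ |
| 250 vs 125 analysed | 3.8 × 10⁻¹³ |
| 150 vs 75 analysed | 1.6 × 10⁻⁷ |

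Even in the last row, the four tests together fail with probability at most 4 × 1.6 × 10⁻⁷ = 6.4 × 10⁻⁷.

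**6. How far the SD assumption can move.** Put an SD of 49 in all four tests: SE = 49 × 0.1010 = 4.95, noncentrality = 30 / 4.95 = 6.06, miss probability = Φ(−4.10) ≈ 2 × 10⁻⁵. Four times that is about 8 × 10⁻⁵, so joint success is still above 99.99%. With an effect of 30, the SD would have to be about 69 before four independent tests gave a product of 96%.

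**7. Check of the 98% step.** If each test had exactly 99% power and the two test statistics were correlated at 0.85, joint power would be 98.4% per frequency and 0.984² ≈ 96.9% for both. Correlation raises the joint figure by less than one point. Nearly all of the gap between 96% and the direct calculation comes from using 99% in place of the actual power.

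**The case against.** The strongest reply is that this is one word. The chain starts with two statements of *at least*, both true, and prints its factors in brackets, so an attentive reader can see that 96% is a product of floors. The error understates power, so nothing is oversold. That stands, and it limits the point to the final sentence.

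Three stronger readings are tempting, and the documents do not support them.

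- **That independence is wrongly assumed.** A reader might infer this from the reported correlation above 85%. But the 96% step multiplies Q2W by QM, and each frequency has its own evolocumab and placebo arm (Protocol 3.1), so independence is justified there. Within a frequency, multiplying 99% by 99% gives a valid lower bound when the two tests are positively correlated, and it is stated as a lower bound. The correlation supports the 98% floor.
- **That the design carries a 1 in 25 risk of failing in a frequency.** A reader might infer this from 96%, but the two *at least* statements just before it rule that reading out.
- **That the plan conceals what drives its size.** Every input is printed, and the text claims only adequate power. It does not say that the sample size was solved from the co-primary comparison.

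It is also fair to object that a replacement figure for all four tests needs an SD the documents do not give. That has to be disclosed, but step 6 shows the conclusion is insensitive to it.

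**Conclusion.** The point holds for the last sentence of the power argument only. The 96% is a valid lower bound and an incorrect approximation. The plan's inputs put the joint probability for all four tests above 99.99%, about 4 percentage points higher than stated. This rests on an effect of 30, an SD of 30, 294 versus 147 analysed, two-sided 0.05 per test, and an assumed SD of 30 for the mean of weeks 10 and 12; any SD up to about 49 gives the same conclusion. The 98% floor per frequency and the multiplication across frequencies are sound. The error is conservative, and sample size, alpha, analysis and conduct are unaffected. It is a minor correction.

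**What to change.** In Protocol 10.2 and SAP 3.2, replace the 96% statement with a directly computed figure: above 99.9% for showing superiority on the co-primary endpoints in both dose frequencies, taking the SD of 30 to apply also to the mean of weeks 10 and 12. Say that this is calculated from the effect, SD and sample size, so that it is not read as a product of the 98% floors. The 98% sentence can stay.

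The minimum acceptable change is *approximately* to *at least* in that sentence. The cost is one sentence, or one phrase, in each document.

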10.3 Access to Individual Subject Treatment Assignments by Amgen or Designees

Blinded individuals will not have access to unblinded information until the study is formally unblinded. Unblinding and potentially unblinding information should not be distributed to the study team, investigators or subjects prior to the study being formally unblinded (eg, the formal unblinding may occur at the final analysis rather than during the primary analysis) except as specified (eg, Section 5.2 and Section 9.2.2).

Individual subject treatment assignments will be maintained by the IVRS/IWRS. Any unplanned unblinding occurring during the study period will be documented and reported in the final clinical study report.

The independent DMC members and Independent Biostatistical Group (IBG) will have access to treatment assignments and subject level data from the clinical trial database. Amgen staff members who are involved in randomization, biological sample management, performing PK, and anti-evolocumab antibody assay analysis will have treatment assignment information but will not have access to subject level data from the clinical trial database.

10.4 Planned Analyses

10.4.1 Data Monitoring Committee (DMC)

An external independent DMC has been established to formally review the accumulating data from this and other completed and ongoing studies with evolocumab to ensure there is no avoidable increased risk for harm to subjects. The independent DMC is chaired by an external academic cardiologist who is an expert in lipids and clinical trials. Analyses for the DMC are provided by the Independent Biostatistical Group (IBG), which is external to Amgen. Details are provided in the DMC charter.

10.4.2 Primary Analysis

The primary analysis will be conducted when all subjects have either completed all the scheduled study visits or have early terminated from the study. At that time, the database will be cleaned, processed and a snapshot will be taken; the study will also be unblinded. Based on the snapshot, efficacy and safety analyses will be performed on

the FAS. Unless specified otherwise, the FAS will be the default analysis set in this study and data will be summarized by randomized treatment group.

Analyses will be performed separately by each dose frequency (Q2W and QM) unless specified otherwise.

10.5 Planned Methods of Analysis

General Considerations

Subject disposition, demographics, baseline characteristics, and exposure to IP will be summarized.

Summary statistics for continuous variables will include the number of subjects, mean, median, standard deviation or standard error, minimum, and maximum. For categorical variables, the frequency and percentage will be given.

Methods of handling missing data for efficacy endpoints will be described throughout this section. Missing data will not be imputed for safety endpoints.

Multiplicity Adjustment Method

In order to preserve the familywise error rate at 0.05, each independent dose frequency (Q2W and QM) will be allocated a significance level of 0.05. For FAS, methods of adjusting for multiplicity due to testing the superiority of evolocumab in combination with atorvastatin to placebo in combination with atorvastatin for both the co-primary and co-secondary efficacy endpoints for the co-primary endpoints within each dose frequency are described in the diagram below.

The multiplicity adjustment method for testing the co-primary and co-secondary efficacy endpoints within each dose frequency using the FAS is described below:

- If the treatment effect differences between evolocumab in combination with atorvastatin and placebo in combination with atorvastatin from the primary analysis of the co-primary endpoints are both significant at a significance level of 0.05, statistical testing of the tier 1 co-secondary efficacy endpoints (as defined in Section 10.1.1.2) will follow the Hochberg procedure at a significance level of 0.005 (Hochberg, 1988).
- 2. If all tier 1 co-secondary efficacy endpoints are significant, the tier 2 co-secondary efficacy endpoints for evolocumab in combination with atorvastatin vs. placebo in combination with atorvastatin will be tested using the Hochberg procedure at a significance level of 0.025.
- 3. If not all tier 1 co-secondary efficacy endpoints are significant, the tier 2 co-secondary efficacy endpoints for evolocumab in combination with atorvastatin vs. placebo in combination with atorvastatin will be tested using the Hochberg procedure at a significance level of 0.02 (Wiens, 2003).

